7.7. Overdose Instructions

Record the actual dose of study drug administered in the source document and on the Dosing eCRF. Record any adverse clinical signs and symptoms associated with a potential overdose on the AE eCRFs. Report signs and symptoms of a potential overdose that meet SAE criteria

(defined in Section 10.1.2) to the Sponsor's Pharmacovigilance group or its designee within 24 hours from the time the investigator first becomes aware of the SAE (see Section 10.2.4). Treat any AE (including SAE) based on standard care for the specific signs and symptoms.

8. **RISKS/PRECAUTIONS**

Refer to the ASTX029 IB for the most current risks and precautions, as well as a list of potential AEs associated with ASTX029 therapy based on nonclinical toxicology studies and clinical findings with other investigational agents in this drug class.

This study represents the first use of ASTX029 in humans, and as with any investigational medicinal product (IMP), subjects may experience reactions or complications that are unknown and therefore unpredictable. Risks to subjects participating in this first evaluation of ASTX029 in a human clinical trial include the potential for adverse reactions.

Based on nonclinical toxicology studies with this molecule, and clinical findings with other investigational agents in this drug class (ERK inhibitors; ie, ulixertinib and GDC-0994) (Sullivan et al 2018; Li et al presentation 2017; Varga et al 2020; Infante et al abstract 2015; Infante et al presentation 2015), the ASTX029 mechanism of action may result in cutaneous AEs (eg, rash, pruritus, dry skin), GI AEs (eg, diarrhea, nausea, vomiting, and esophagitis), fatigue, peripheral and periorbital edema, LVEF decrease, potential arrhythmias, visual disturbances, and liver enzyme elevation.

The potential for these AEs warrants frequent monitoring of subjects participating in clinical trials of ASTX029 until the safety profile is further understood. In particular, clinical signs and/or symptoms of cutaneous, ocular, GI, and liver toxicities and LVEF decrease will be closely monitored, evaluated, and managed during the study (Appendix 4, Appendix 5, Appendix 6, Appendix 7, and Appendix 8 respectively).

9. STUDY ASSESSMENTS AND PROCEDURES

9.1. Preliminary Clinical Activity Assessments

Measurable disease according to RECIST v1.1 (Appendix 3) will be assessed using CT or MRI scans at baseline (screening), every 2 cycles (\pm 7 days) for the first 4 cycles, and then every 4 cycles (\pm 1 cycle) thereafter until clinical and/or radiographic disease progression, death, or the subject withdraws consent. Tumor markers (if applicable) should be measured at the same time points as the time points for radiological assessments.

For subjects whose disease is not measurable using RECIST v1.1, disease status must be reliably and consistently followed using another generally acceptable method.

9.2. Pharmacokinetic/Pharmacodynamic/Biomarker Assessments

9.2.1. Pharmacokinetic Assessments

Serial blood samples for Phase 1 will be collected over a 24-hour period at specified time points postdose for PK analysis on C1D1, Cycle 1 Day 2 (C1D2), Cycle 2 Day 1 (C2D1), and Cycle 2 Day 2 (C2D2) for Regimen 1 (Table 4) and on C1D1, C1D2, Cycle 1 Day 14 (C1D14), and Cycle 1 Day 15 (C1D15) for Regimen 2 (Table 5).

Serial blood samples for Phase 2 will be collected on C1D1, C1D2, C2D1, and Cycle 3 Day 1 (C3D1) for Regimen 1 (Table 6) and on C1D1, C1D2, C1D14, C1D15, and C3D1 for Regimen 2 (Table 7).

Additional ad hoc blood sample(s) may be collected, per investigator discretion, for PK measurement at any time, including after the last dose, if there is a suspected safety issue.

ASTX-029 plasma concentration data will be used to determine PK parameters, including AUC, C_{max} , C_{min} , T_{max} , and $t_{\frac{1}{2}}$, in all subjects initially during Cycle 1 (both regimens) and Cycle 2 (Regimen 1), if data are evaluable. Metabolites of ASTX029 may be investigated if applicable. It is essential that the actual time and date of sample collection relative to the administration of study treatment be recorded in the subject's eCRF. Nominal PK blood sampling times and collection windows should be adhered to as closely as possible.

During the course of the study, as data emerge and improve the understanding of PK of ASTX029, sample collection times may be modified. Blood sample preparation and plasma sample storage details are provided in the laboratory manual.

Table 4:Phase 1: Plasma Collection Schedule for Pharmacokinetic Analysis
(Regimen 1)

Study Day	Dosing Day?	Time Point ^a	Hours Postdose
C1D1	Yes	Predose	$\begin{array}{l} 0.5 \ (\pm 5 \ m), \ 1.0 \ (\pm 5 \ m), \\ 2.0 \ (\pm 10 \ m)^b, \ 3.0 \ (\pm 10 \ m), \\ 4.0 \ (\pm 10 \ m), \ 6.0 \ (\pm 20 \ m), \\ 8.0 \ (\pm 30 \ m) \end{array}$
C1D2	Yes	24 ±1.0 h after C1D1 dose (prior to C1D2 dose)	

Study Day	Dosing Day?	Time Point ^a	Hours Postdose
C2D1	Yes	Predose	$\begin{array}{l} 0.5 \ (\pm 5 \ m), \ 1.0 \ (\pm 5 \ m), \\ 2.0 \ (\pm 10 \ m)^b, \ 3.0 \ (\pm 10 \ m), \\ 4.0 \ (\pm 10 \ m), \ 6.0 \ (\pm 20 \ m), \\ 8.0 \ (\pm 30 \ m) \end{array}$
C2D2	Yes	24 ±1.0 h after C2D1 dose (prior to C2D2 dose)	
Ad hoc PK sample (including trough sample, ie, ~24 h post last dose if safety event suspected)			Per investigator discretion

CxDx=Cycle x Day x; ECG=electrocardiogram; h=hour(s); m=minute(s); PK=pharmacokinetic.

^a On dosing days, collect predose samples within 60 minutes prior to administration of study treatment.

^b It is recommended that the 2-hour postdose ECG be performed before PK sample collection.

Table 5:Phase 1: Plasma Collection Schedule for Pharmacokinetic Analysis
(Regimen 2)

Study Day	Dosing Day?	Time Point ^a	Hours Postdose
C1D1	Yes ^a	Predose	$\begin{array}{c} 0.5 \ (\pm 5 \ m), \ 1.0 \ (\pm 5 \ m), \\ 2.0 \ (\pm 10 \ m)^b, \ 3.0 \ (\pm 10 \ m), \\ 4.0 \ (\pm 10 \ m), \ 6.0 \ (\pm 20 \ m), \\ 8.0 \ (\pm 30 \ m) \end{array}$
C1D2	Yes ^a	24 ±1.0 h after C1D1 dose (prior to C1D2 dose)	
C1D14	Yes ^a	Predose	$\begin{array}{c} 0.5 \ (\pm 5 \ m), \ 1.0 \ (\pm 5 \ m), \\ 2.0 \ (\pm 10 \ m)^b, \ 3.0 \ (\pm 10 \ m), \\ 4.0 \ \ (\pm 10 \ m), \ 6.0 \ (\pm 20 \ m), \\ 8.0 \ (\pm 30 \ m) \end{array}$
C1D15	No	24 ± 1.0 h after C1D14 dose	
Ad hoc PK sample (including trough sample, ie, ~24 h post last dose if safety event suspected)			Per investigator discretion

CxDx=Cycle x Day x; ECG=electrocardiogram; h=hour(s); m=minute(s); PK=pharmacokinetic.

^a On dosing days, collect predose samples within 60 minutes prior to administration of study treatment.

^b It is recommended that the 2-hour postdose ECG be performed before PK sample collection.

Table 6:Phase 2: Plasma Collection Schedule for Pharmacokinetic Analysis
(Regimen 1)

Study Day	Dosing Day?	Time Point ^a	Hours Postdose
C1D1	Yes	Predose	0.5 (±5 m), 1.0 (±5 m), 2.0 (±10 m) ^b , 3.0 (±10 m), 4.0 (±10 m), 6.0 (±20 m), 8.0 (±30 m)
C1D2	Yes	24 ±1.0 h after C1D1 dose (prior to C1D2 dose)	
C2D1	Yes	Predose	2.0 (±10 m) ^b
C3D1	Yes	Predose	0.5 (±5 m), 1.0 (±5 m), 2.0 (±10 m), 4.0 (±10 m), 8.0 (±30 m)

Study Day	Dosing Day?	Time Point ^a	Hours Postdose
Ad hoc PK sample (including trough sample, ie, ~24 h post last dose if safety event suspected)			Per investigator discretion

CxDx=Cycle x Day x; ECG=electrocardiogram; h=hour(s); m=minute(s); PK=pharmacokinetic.

^a On dosing days, collect predose samples within 60 minutes prior to administration of study treatment.

^b It is recommended that the 2-hour postdose ECG be performed before PK sample collection.

Table 7:Phase 2: Plasma Collection Schedule for Pharmacokinetic Analysis
(Regimen 2)

Study Day	Dosing Day?	Time Point ^a	Hours Postdose
C1D1	Yes ^a	Predose	$\begin{array}{c} 0.5 \ (\pm 5 \ m), \ 1.0 \ (\pm 5 \ m), \\ 2.0 \ (\pm 10 \ m)^b, \ 3.0 \ (\pm 10 \ m), \\ 4.0 \ (\pm 10 \ m), \ 6.0 \ (\pm 20 \ m), \\ 8.0 \ (\pm 30 \ m) \end{array}$
C1D2	Yes ^a	24 ± 1.0 h after C1D1 dose (prior to C1D2 dose)	
C1D14	Yes ^a	Predose	$\begin{array}{c} 0.5 \ (\pm 5 \ m), \ 1.0 \ (\pm 5 \ m), \\ 2.0 \ (\pm 10 \ m)^b, \ 3.0 \ (\pm 10 \ m), \\ 4.0 \ (\pm 10 \ m), \ 6.0 \ (\pm 20 \ m), \\ 8.0 \ (\pm 30 \ m) \end{array}$
C1D15	No	24 ± 1.0 h after C1D14 dose	
C3D1	Yes	Predose	0.5 (±5 m), 1.0 (±5 m), 2.0 (±10 m), 4.0 (±10 m), 8.0 (±30 m)
Ad hoc PK sample (including trough sample, ie, ~24 h post last dose if safety event suspected)			Per investigator discretion

CxDx=Cycle x Day x; ECG=electrocardiogram; h=hour(s); m=minute(s); PK=pharmacokinetic.

^a On dosing days, predose samples are to be collected within 60 minutes prior to administration of study treatment

^b It is recommended that the 2-hour postdose ECG be performed before PK sample collection.

9.2.2. Pharmacodynamic and Biomarker Assessments

Assessment of target engagement and biomarker analyses will be performed in blood and tumor tissue biopsies. Biomarker investigations will include the following:

- Demonstration of target engagement in fresh tumor tissue biopsies (when available) (eg, pRSK and pERK inhibition following ASTX029 treatment).
- Evaluation of cancer cell proliferation and induction of apoptosis in fresh tumor tissue biopsies (when available).
- Suppression of mutant clones in ctDNA.
- Identification of potential biomarkers of ASTX029 activity (DNA, RNA, or protein) in blood and tumor tissue biopsies (archival and fresh biopsies, when available).

Biomarker analyses will be performed by methods including immunohistochemistry, reverse transcription polymerase chain reaction (RT-PCR), next-generation sequencing, and possibly others.

Blood samples will be collected for biomarker analysis at the time points indicated in Table 8. Details of blood sample collection and handling procedures are provided in the laboratory manual.

If a FFPE archived tumor tissue is available, it will be obtained for use in this study during screening. In addition, collection of new (or fresh) tumor biopsies is encouraged (optional) in Phase 1 Part A and Phase 2 and mandatory in Phase 1 Part B of the study at the time points indicated in Table 9.

Archived tissue and fresh biopsies collected at screening will be used to characterize the genetic background of the tumor, confirm mutational status, and identify potential additional biomarkers of response to ASTX029; biopsies collected on treatment will be used to establish target engagement in tumor tissue and changes induced by ASTX029 treatment. At each time point (if safe and feasible), at least 2 biopsy cores will be collected (1 to be fresh-frozen and 1 to be FFPE). The subject must sign a biopsy ICF. A posttreatment biopsy sample need not be collected if a pretreatment biopsy (fresh) is not available for comparison. Details of biopsy tissue collection and handling procedures are provided in the laboratory manual.

Study Day	Dosing Day?	Samples	Time Point
Screening	No	Germline DNA (PBMC), ctDNA	
C1D1	Yes	ctDNA	Predose ^a
C2D1	Yes	ctDNA	Predose ^a
Day 1 of every cycle thereafter	Yes	ctDNA	Predose ^a
Treatment Termination visit	No	ctDNA	

 Table 8:
 Sample Collection Schedule for Biomarker Analyses

CxDx=Cycle x Day x; ctDNA=circulating tumor DNA; PBMC=peripheral blood mononuclear cell.

^a On dosing days, predose samples are to be collected within 60 minutes prior to administration of study treatment.

Table 9: Tumor Tissue Collection Schedule for Biomarker Analyses
--

Study Day	Dosing Day?	Samples	Time Point
Archival	No	FFPE	
Screening	No	FFPE, Frozen	
C2D8 (±1 day)	Yes	FFPE, Frozen	4.0 h (±1 h) postdose

C2D8=Cycle 2 Day 8; h=hour(s); FFPE=formalin-fixed paraffin embedded.

If archived tumor tissue (FFPE) is available, it will be requested for use in this study during screening. In addition, collection of fresh tumor biopsies is encouraged (optional) in Phase 1 Part A and Phase 2, and mandatory in Phase 1 Part B.

9.2.3. Total Volume of Blood Samples to Be Drawn

The estimated amount of blood to be collected for PK, biomarker investigations, and routine monitoring of hematology, coagulation, and serum chemistry during any cycle will not exceed 165 mL.

9.3. Safety Assessments

At each study visit, safety will be monitored by recording AEs, SAEs, DLTs, and concomitant medications; additional assessments that may be performed at selected visits include complete or symptom-directed physical examinations (PEs), weight, height, vital signs, ECOG performance status, 12-lead ECGs, clinical laboratory tests (including hematology, serum chemistry, urinalysis, and other tests [coagulation tests] as applicable), and ECHO/MUGA scans (see Table 11 and Table 12 for the complete schedules of events for Regimen 1 and Regimen 2, respectively). General information regarding the definition, evaluation, recording, and reporting of AEs and SAEs is provided in Section 10. Additional information regarding AEs specific to this protocol are provided below.

9.3.1. Adverse Events

The AEs should be captured from the time of first dose until 30 days after the last dose of study treatment or the start of an alternative treatment, whichever occurs first. The AEs that occur during the screening period and are considered related to screening procedures, as well as all related SAEs occurring beyond 30 days from the last dose of study treatment, will also be captured. Any SAEs will be followed until they have resolved or are stable.

The following events will be recorded in the eCRF as AEs:

- Adverse events of any severity grade (including changes from screening).
- Clinically significant abnormal findings during clinical assessments, including PEs and vital signs.
- Clinically significant abnormal ECG readings and any clinically significant ECHO/MUGA results.
- Spontaneous subject reports.
- Baseline medical conditions and AEs, other than the primary disease under evaluation, that worsen in severity or frequency during the study.

Clinical hematology, coagulation, serum chemistry, and urinalysis results that are outside of normal ranges but are not considered by the investigator to be clinically significant will not be reported as AEs.

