- ^k Record all medications a subject takes starting from 14 days before study treatment initiation and ending 30 days after the last dose of study treatment. Record screening procedure-related AEs that occur before the start of study treatment and new AEs from the start of study treatment until 30 days after the last dose of study treatment or until the subject starts a new cancer treatment, including new investigational treatment, whichever occurs first. Also record screening procedure-related AEs that occur before the start of study treatment. Refer to Section 10.2.
- ¹ Hematology must include CBC with either manual or automated differential and platelet counts; if both are done, the manual counts will be entered into the eCRF (Table 10). C1D1 hematology evaluations do not need to be repeated if screening tests are within 4 days prior to first dose of ASTX029. On C1D1, all hematology evaluations must meet study entry criteria before dosing.
- ^m Hematology, chemistry, coagulation, and urinalysis tests may be performed on the day before the visits and the pregnancy test may be performed within 24 hours before the start of study treatment Cycles 1-6 if more convenient.
- ⁿ Collect PTT and prothrombin time (or INR) at screening, predose on Day 1 of each cycle, and at the Tx Term visit. The C1D1 coagulation evaluations do not need to be repeated if screening tests are done within 4 days prior to first dose of ASTX029.
- Serum chemistry must include the analytes listed in Table 10. The C1D1 chemistry evaluations do not need to be repeated if screening tests are within 4 days prior to first dose of ASTX029. On C1D1, all chemistry evaluations must meet study entry criteria before dosing.
- ^p Urinalysis includes dipstick test (if available) and microscopic examination (if indicated) (Table 10). The C1D1 urinalysis evaluations do not need to be repeated if screening tests are within 4 days prior to the first dose of ASTX029.
- ^q Pregnancy test: to be performed at screening, within 24 hours before the start of Cycles 1 through 6, at least monthly during treatment thereafter, and at the Tx Term visit (only for women of child-bearing potential).
- ^r See Table 4 and Table 6, respectively (Section 9.2.1), for the complete PK blood draw schedule for Phase 1 and Phase 2.
- ^s Collect PK blood samples in Phase 1 only; see Table 4.
- ^t Collect PK blood samples in Phase 2 only; see Table 6.

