10.2. Adverse Event Reporting and Descriptions

Record new AEs from the start of study treatment until 30 days after the last dose of study treatment or until the subject starts new anticancer treatment, including new investigational treatment, whichever occurs first. Also record screening procedure-related AEs that occur before the start of study treatment. Collection of AEs may also continue until the decision is made to permanently discontinue study treatment.

Record all AEs either observed by the investigator or one of the medical collaborators, or reported by the subject spontaneously, or in response to the direct question below, in the AEs section of the subject's eCRF, in the source document, and if applicable, record on the SAE Report form. Whenever possible, the investigator should group signs and symptoms (including laboratory tests or other results of diagnostic procedures) into a single diagnosis under a single term. For example, cough, rhinitis, and sneezing might be reported as "upper respiratory infection" or a pulmonary infiltrate, positive sputum culture and fever might be reported as "pneumonia."

To optimize consistency of AE reporting across centers, ask the subject a standard, general, non-leading question to elicit any AEs (such as "Have you had any new symptoms, injuries, illnesses since your last visit?").

Death is an outcome of an SAE and usually not itself an SAE, unless it is death with no identifiable cause or event. In all other cases, record the cause of death as the SAE. Investigators will assess the status of previously reported, and occurrence of new AEs and SAEs at all subject evaluation time points during the study.

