10.2.4. Reporting Requirements for Serious Adverse Events (SAEs)

All SAEs regardless of causality will be reported by the investigator to the Sponsor through the 30-day period after the last dose of study treatment. Deaths and SAEs occurring after the 30-day safety follow-up period AND considered related to study treatment or study procedures must also be reported until the end of the study or subject death.

Report all SAEs (initial and follow-up information) on the SAE Report form and email it to the Sponsor's Pharmacovigilance group or designee, within 24 hours of learning of the event or information (see below). The Sponsor may request follow-up and other additional information from the investigator (eg, hospital admission or discharge notes, laboratory results).

Sponsor's Pharmacovigilance Group Contact Information					
PRIMARY CONTACT: email	[contact]				

Report all deaths with the primary cause of death as the SAE term, as death is the outcome of the event, not the event itself. If an autopsy was performed, report the primary cause of death on the autopsy report as the SAE term. Forward autopsy and postmortem reports to the Sponsor's Pharmacovigilance group or designee, as outlined above.

If study treatment is discontinued, temporarily suspended, or dose reduced because of an SAE, include this information in the SAE Report form.

Suspected Unexpected Serious Adverse Reactions (SUSARs) are SAEs that qualify for mandatory expedited safety reporting to regulatory authorities where the SAE is suspected to be caused by the study treatment and is considered unexpected (ie, not listed as expected in the Reference Safety Information section of the current IB, clinical study protocol, or approved

labeling for marketed drugs). In this case, the Sponsor's Pharmacovigilance group or designee will report to the relevant regulatory authorities and forward a formal notification describing the SUSAR to investigators, according to regulatory requirements. Each investigator must then notify his or her IRB/IEC of the SUSAR as required by local regulatory authorities and in accordance with IRB/IEC policy.

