#### 7.6.2 Adverse Events

Adverse events reported by study subjects or observed by investigators will be mapped to the appropriate System Organ Class (SOC) and Preferred Term (PT) according to the Medical Dictionary for Regulatory Activities (MedDRA). Severity of AEs will be graded using Common Terminology Criteria for Adverse Events (CTCAE) version 4.03 (protocol Appendix 2).

TEAEs are defined as events that first occurred or worsened on or after the date of the first dose of study treatment until 30 days after the last dose of study treatment or until the start of a post-treatment alternative anti-cancer treatment, whichever occurs first, with the following exceptions: events that occurred after 30 days beyond the last dose of study treatment or the start of a post-treatment alternative anti-cancer treatment will also be considered treatment-emergent if the events are both serious and related to the study treatment. For the purpose of determining whether an AE is a TEAE, incomplete AE start and stop dates will be imputed conservatively following the data programming conventions as detailed in the Taiho Data Programming Standards.

All AE data collected in the study database with an AE start date on or before the data cutoff date will be included in the data listings, including those that are not treatment emergent. Only TEAEs will be included in the AE summary tables.

An overall safety summary table containing counts and percentages of subjects with any AE, any AE Grade ≥3, AE leading to treatment discontinuation, any SAE, and subcategories of SAEs (fatal SAEs) will be produced.

Related events are those that the Investigator considered to be related to study treatment as described in the study protocol. All summaries of AEs will be summarized by cohorts and all cohorts combined within regimen within parts (A&B), and within Phase (I&II). Tables may be combined when space allows.

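### Related SAEs between an early switch to new anticancer treatment and day 30 have no eCRF capture instruction, although the SAP counts them as TEAEs

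*Protocol*

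**What the plan says.** Three sets of rules bear on serious events after the last dose.

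**Capture.** Protocol 9.3.1 collects AEs "until 30 days after the last dose of study treatment or the start of an alternative treatment, whichever occurs first". Its only later provision for treated subjects is for "all related SAEs occurring beyond 30 days from the last dose of study treatment". Section 10.2, which also carries the instruction to enter AEs in the eCRF, uses the same cut: "until 30 days after the last dose of study treatment or until the subject starts new anticancer treatment". Footnote k of Table 11 agrees ("until 30 days after the last dose of study treatment or until the subject starts a new cancer treatment"), Table 12 repeats it, and the note in Table 13 for the extension phase has the same effect. Neither 10.2, nor footnote k, nor the Table 13 note adds an exception for related SAEs.

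**Reporting.** Protocol 10.2.4 has no cut at new treatment: "All SAEs regardless of causality will be reported by the investigator to the Sponsor through the 30-day period after the last dose". After that, "Deaths and SAEs occurring after the 30-day safety follow-up period AND considered related to study treatment or study procedures must also be reported". The route named there is the SAE Report form, emailed to pharmacovigilance. Section 5.4.1 likewise sets minimum safety follow-up at 30 days after the last dose without mentioning new treatment.

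**Analysis.** Protocol 11.7 ends the TEAE window at day 30 or alternative anticancer treatment, whichever is earlier, and leaves detail to the SAP. SAP 7.6.2 keeps both cut-offs but adds that events after either one "will also be considered treatment-emergent if the events are both serious and related to the study treatment". Its listings use AE data held in the study database, and its summary tables use TEAEs only.

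**The concern.** The capture rule has two possible end points, but its exception for related SAEs is tied to only one of them. When new anticancer treatment comes first, general AE capture closes at the switch and capture of related SAEs does not reopen until day 30 has passed. The SAP ties its exception to both end points, so for this interval it tabulates events that no section tells the site to enter in the eCRF.

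The situation is foreseeable. Section 5.4.1 says subjects whose disease progresses should come off study treatment, and the schedule allows the 30-day safety visit to be brought forward to within 3 days before new cancer treatment. No safety visit need then fall in the gap. The next planned contact is the 3-monthly telephone call in 9.4.15, which lists only survival and date of progression.

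At stake is the completeness of the SAE and related-SAE tables for a first-in-human drug. Any error runs in one direction, towards too few late serious related events.

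**Working it through.** The documents state no figure to reproduce, so the check sets the windows side by side. Let day 0 be the last dose and s the day on which new anticancer treatment starts.

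**Inputs**
- 9.3.1, 10.2, footnote k of Tables 11 and 12, Table 13 note: AE capture to the earlier of day s and day 30.
- 9.3.1 exception: related SAEs after day 30.
- 10.2.4: all SAEs to day 30, then related SAEs.
- SAP 7.6.2: TEAE up to the earlier of day s and day 30; after either cut-off, TEAE if serious and related.

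**Length of the gap.** If s is below 30, the interval with no capture instruction runs from day s to day 30, so its length is 30 − s. If s is 30 or more, there is no gap. The documents do not give s. Over an assumed range:
- s = 1: 30 − 1 = 29 days
- s = 7: 30 − 7 = 23 days
- s = 14: 30 − 14 = 16 days
- s = 21: 30 − 21 = 9 days

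**Worked case, s = 10**

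| Event | Captured under 9.3.1 | Reported under 10.2.4 | TEAE under SAP 7.6.2 |
|---|---|---|---|
| Related SAE, day 20 | No | Yes | Yes |
| Unrelated SAE, day 20 | No | Yes | No |
| Related SAE, day 35 | Yes | Yes | Yes |

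The first row is the defect. A related SAE on day 20 is outside capture, while the same event on day 35 is inside it. That ordering cannot be intended and reads as a drafting omission. The second row shows that the TEAE tables lose nothing for unrelated SAEs; for those the issue is listings and reconciliation. The third row shows that the beyond-day-30 part of the SAP exception has its data.

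**Wording checks.** Section 9.3.1 speaks of alternative treatment in general; 10.2, 11.7, the schedule footnotes and the SAP show that anticancer treatment is meant. The SAP sentence could be read as 30 days beyond either date, but the clause before it treats day 30 and the start of new treatment as separate cut-offs, which supports the reading used here. Under 11.7 alone the day-20 related SAE would not be a TEAE. SAP 1.0 says the SAP supersedes the protocol's analysis plan, so 7.6.2 governs, although SAP 7.9 does not list this exception as a change.

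**The case against.** The best reply is that the SAE-specific rule already covers the interval. Section 9.3 sends recording and reporting of SAEs to Section 10, and 10.2.4 requires every SAE through day 30, whatever its cause, within 24 hours of the site learning of it. On that reading 9.3.1 is a general AE window with a longer SAE rule beside it. Moreover, 10.2 treats the SAE Report form as an addition to the eCRF, and nothing says that an SAE reported under 10.2.4 stays out of the eCRF.

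Much of this stands. The events are not lost to the sponsor, and their absence from the eCRF is a possibility rather than a stated outcome. The missing visit also matters less, because reporting depends on learning of the event. What does not stand is that the gap is closed: 10.2.4 names only the form sent to pharmacovigilance, and the eCRF instruction sits in 10.2 under the shorter window. A site following 9.3.1 and 10.2 literally has no reason to enter the day-20 event in the database that the SAP tabulates.

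Three stronger readings may tempt a reader, and the documents support none of them.
- That the SAP exception has no data at all. Section 9.3.1 expressly captures related SAEs beyond day 30, including in subjects who switched earlier.
- That fatal events are lost. Deaths are collected in survival follow-up (9.4.15) and listed with primary cause (SAP 7.0), and an unrelated fatal SAE after the switch is not a TEAE however it is captured.
- That a percentage of post-treatment safety time goes unobserved. The documents give neither a switching rate nor a switch day, and 10.2.4 covers SAEs throughout that time.

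**Conclusion.** The mismatch is real, narrow and wrong as written. It affects related SAEs in subjects who start new anticancer treatment before day 30, between the switch and day 30. For these the SAE and related-SAE tables can undercount and may not reconcile with the safety database. The interval is 30 − s days per switching subject. The number of events affected cannot be derived from the documents and may be small.

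The conclusion assumes that sites follow the capture sections literally and that the tables draw on the study database without SAEs being added from the safety database. If sites already enter every SAE reported under 10.2.4 in the eCRF, the tables are unaffected and only the text is inconsistent. Because the correction is cheap and the possible error lies in one direction, it should be made.

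**What to change.** In 9.3.1, let either cut-off trigger the exception: keep "all related SAEs occurring beyond 30 days from the last dose of study treatment" and add: or after the start of alternative anticancer treatment. This matches SAP 7.6.2. Align 10.2, footnote k of Tables 11 and 12, and the Table 13 note with it. State in 10.2 or 10.2.4 that SAEs reported under 10.2.4 are also entered in the AE eCRF.

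The cost is a few lines of protocol text plus some added data entry and reconciliation. Causality assessment adds nothing new, since 10.2.2 already requires it for every AE and SAE. New wording will not recover events from windows that have already closed. SAP 6.0 puts the study start in Q2 2018 and protocol Section 12 plans about 55 months of recruitment, so planned recruitment ends around the turn of 2022-23, while Amendment 5.0 is dated 23 May 2024. For subjects already off treatment, the remedy is to reconcile the safety database against the AE eCRF before the final tables are produced.
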